# 6.1.1.3 Radiofrequency Research Coils for 3T and 7T MRI

Research coils used during MRI scans under this protocol are considered non-significant risk (NSR) devices.

Criteria establishing research coils as NSR devices:

a. is intended as an implant and presents a potential for serious risk to the health, safety, or welfare of a subject

Research coils are not an implantable device.

b. is purported or represented to be for a use in supporting or sustaining human life and presents a potential for serious risk to the health, safety, or welfare of a subject

Research coils are not for use in supporting or sustaining human life. They do not present a potential for serious risk to the health, safety, or welfare of participants when used as described in this protocol.

c. is for a use of substantial importance in diagnosing, curing, mitigating, or treating disease, or otherwise preventing impairment of human health and presents a potential for serious risk to the health, safety, or welfare of a subject

Research coils, as used under this protocol, are not of substantial importance in diagnosing, curing, mitigating, or treating disease, or otherwise preventing impairment of human health and does not present a potential for serious risk to the health, safety or welfare of a subject.

d. otherwise presents a potential for serious risk to the health, safety or welfare of a subject

Research coils, as used under this protocol, do not present a potential for serious risk to the health, safety, or welfare of a subject. The research coils are used within the FDA/IEC safety limits for MRI devices.

#### 6.1.1.4 Image Reconstruction and Analysis Software for 3T and 7T MRI

Image reconstruction and analysis software used during MRI scans under this protocol are considered non-significant risk (NSR) devices.

Criteria establishing image reconstruction and analysis software as NSR devices:

a. is intended as an implant and presents a potential for serious risk to the health, safety, or welfare of a subject

Image reconstruction and analysis software are not implantable devices.

b. is purported or represented to be for a use in supporting or sustaining human life and presents a potential for serious risk to the health, safety, or welfare of a subject

Image reconstruction and analysis software are not for use in supporting or sustaining human life. They do not present a potential for serious risk to the health, safety, or welfare of participants when used as described in this protocol.

c. is for a use of substantial importance in diagnosing, curing, mitigating, or treating disease, or otherwise preventing impairment of human health and presents a potential for serious risk to the health, safety, or welfare of a subject

Image reconstruction and analysis software, as used under this protocol, are not of substantial importance in diagnosing, curing, mitigating, or treating disease, or otherwise preventing impairment of human health and does not present a potential for serious risk to the health, safety or welfare of a subject.

d. otherwise presents a potential for serious risk to the health, safety or welfare of a subject

Image reconstruction and analysis software, as used under this protocol, do not present a potential for serious risk to the health, safety, or welfare of a subject. The software are used within the FDA/IEC safety limits for MRI devices.

# 6.1.2 Dosing and Administration

The starting dose will be 100 mg/day (given as a single AM dose approximately 30 minutes after start of breakfast) and the treatment target for all participants will be 100 mg/day unless tolerability issues ensue. The dose of TS-161/placebo will remain at 100 mg/day in subjects until the end of the study. If subjects are unable to tolerate the current dose, then the dose may be decreased down to 50 mg/day for one week at which time the dose may be increased back to 100 mg/day if response criteria are not met and side effects are tolerable. In case of continued side effects at 100 mg/day, the dose may be lowered to 50 mg/day until the end of the study. Subjects who are unable to tolerate the lowest allowable dose of study medication (50 mg/day) will be discontinued from the study. No dose increases will be allowed two weeks after the start of each research condition (Days 14 and 49) to allow ample time to evaluate the effect of the drug. Only licensed independent practitioners who are investigators on this protocol will be able to make dosing decisions. The maximum daily dose of TS-161 administered in this study will be 100 mg/day.

## 6.2 PREPARATION/HANDLING/STORAGE/ACCOUNTABILITY

Preparation, handling, storage, and accountability will be handled by the Clinical Center's Investigational Drug Management and Research Section (IDMRS) in accordance with the Investigational Brochure (IB).

## 6.3 ACQUISITION AND ACCOUNTABILITY

The study drug and placebo will be provided by the manufacturer, Taisho Pharmaceutical Co., Ltd, in accordance with a CRADA (see Collaborative Agreements). The study site pharmacist(s) responsible for study drug dispensation.

Study personnel will pick up the study intervention or the control product from the NIH pharmacy the day of the study visit. Any unused study intervention or control product will be returned to the NIH pharmacy for disposal.

#### 6.4 FORMULATION, APPEARANCE, PACKAGING, AND LABELING

The name of the participant, name of the study, participant number, directions for administration, day of study visit, and the signature of the physician should appear on the study intervention and the control product.

# 6.4.1 Product Storage and Stability

## 6.4.2 Preparation

Instructions for the preparation of study drugs are provided in a separate manual.

#### 6.5 MEASURES TO MINIMIZE BIAS: RANDOMIZATION AND BLINDING

A randomization code will be generated by the unblinded statistician. The study site pharmacist(s) responsible for study drug dispensation will also be unblinded.

#### 6.6 STUDY INTERVENTION COMPLIANCE

The study drug will be administered to participants on the inpatient unit to ensure adherence to the protocol.

## 6.7 CONCOMITANT THERAPY

For this protocol, a prescription medication is defined as a medication that can be prescribed only by a properly authorized/licensed clinician. Medications to be reported in the Case Report Form (CRF) are concomitant prescription medications, over-the-counter medications and supplements. See Appendix B: Drugs Allowed and Not Allowed.

# 7 STUDY INTERVENTION DISCONTINUATION AND PARTICIPANT DISCONTINUATION/WITHDRAWAL

#### 7.1 DISCONTINUATION OF STUDY INTERVENTION

Discontinuation from TS-161 does not mean discontinuation from the study, and remaining study procedures should be completed as indicated by the study protocol. If a clinically significant finding is identified after enrollment (including, but not limited to changes from baseline), the investigator or qualified designee will determine if any change in participant management is needed. Any new clinically relevant finding will be reported as an AE.

To the extent possible, data to be collected at the time of study intervention discontinuation are those intended for the final day of the study (see Schedule of Events).

Participants are free to withdraw from participation in the study at any time upon request.

An investigator may discontinue or withdraw a participant from the study for the following reasons:

- Completion of study intervention
- Disease progression which requires discontinuation of the study intervention
- If any clinical AEs, laboratory abnormality, or other medical condition or situation occurs such that continued participation in the study would not be in the best interest of the participant. Examples include:
  - Extreme changes in vital signs
  - Persistent systolic blood pressure (SBP) > 165 mm Hg, diastolic blood pressure (DBP) > 100 mm Hg, SBP < 80 (symptomatic), pulse >130, pulse < 45 (symptomatic), SaO2 < 90%, and T > 39 degrees C
- Investigator discretion
- Positive pregnancy test
- Participant unable to receive TS-161 for 3 weeks.

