Day 44	Study Drug Administration: TS-161/ Placebo (100mg or 50mg) V Clinical Evaluations: Orthostatic Vital Signs					
Day 45	Study Drug Administration: TS-161/ Placebo (100mg or 50mg) V Clinical Evaluations: Orthostatic Vital Signs					
Day 46	Study Drug Administration: TS-161/ Placebo (100mg or 50mg) V Clinical Evaluations: Orthostatic Vital Signs					
Day 47	Study Drug Administration: TS-161/ Placebo (100mg or 50mg) V Clinical Evaluations: Orthostatic Vital Signs					
Day 48	Study Drug Administration: TS-161/ Placebo (100mg or 50mg) v Clinical Evaluations: Orthostatic Vital Signs					
Day 49	Clinical Rating Scales ii AE Assessments Sample Collection: Research Blood, PK Blood, Safety Labs iii ,エラー! ブックマークが定義されていません。 Study Drug Administration: TS-161/ Placebo (100mg or 50mg) v Clinical Evaluations: Orthostatic Vital Signs					
Day 50	Study Drug Administration: TS-161/ Placebo (100mg or 50mg) Clinical Evaluations: Orthostatic Vital Signs					
Day 51	Study Drug Administration: TS-161/ Placebo (100mg or 50mg) Clinical Evaluations: Orthostatic Vital Signs					
Day 52	Study Drug Administration: TS-161/ Placebo (100mg or 50mg)					

Timepoint i	Procedures					
	Clinical Evaluations: Orthostatic Vital Signs					
Day 53	Study Drug Administration: TS-161/ Placebo (100mg or 50mg) Clinical Evaluations: Orthostatic Vital Signs					
Day 54	Study Drug Administration: TS-161/ Placebo (100mg or 50mg) Sample Collection: Urine pregnancy test Clinical Evaluations: Orthostatic Vital Signs					
Day 55	Sample Collection: Research Blood, PK Blood Neurocognitive Battery Imaging: fMRI/MRS, MEG Study Drug Administration: TS-161/ Placebo (100mg or 50mg) Clinical Evaluations: Orthostatic Vital Signs					
Day 56 (or End of Study)	Clinical Rating Scales ii AE Assessments Sample Collection: Safety Labs iii,エラー! プックマークが定義されていません。 Clinical Evaluations: Urine Toxicology, Orthostatic Vital Signs, Weight, Height, ECG, Physical Exam					
Standard Treatment						
Up to 2 months	Standard Treatment					

i Allow up to 3 hours for procedures scheduled on the same day. Allow up to 3 days on procedures scheduled on different days to accommodate changes to the schedule. Some procedures may not be performed due to unforeseen technical or scheduling problems.

<sup>ii See the Schedule of Clinical Rating Scales for specific scales used.

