# 1.4 SCHEDULE OF CLINICAL RATING SCALES

Timepoint i	C-SSRS- lifetime, FHS	BPRS, YMRS	CADSS	C-SSRS, HDRS, HAM-A, PANAS, SHAPS, SSI, TEPS	MADRS			
Study Phase I								
Days -8 to -2	X ii							
Day -1	$X^{ii}$	X	X	X	X			
Study Phase II								
Research Condition 1								
Day 0								
-60 min					X			
+230 min		X	X	X	X			
Day 1		X	X	X	X			
Day 2			X	X	X			
Day 3			X	X	X			
Day 7			X	X	X			
Day 14			X	X	X			
Day 21		X	X	X	X			
Research Condition	on 2							
Day 34		X	X	X	X			
Day 35								
-60 min					X			
+230 min		X	X	X	X			
Day 36		X	X	X	X			
Day 37			X	X	X			
Day 38			X	X	X			
Day 42			X	X	X			
Day 49			X	X	X			
Day 56 (or End of Study)		X	X	X	X			

<sup>i Allow up to 3 hours on same day for procedures scheduled on the same day.

 $^{\mathrm{ii}}$  These will be completed once during Phase I, if not previously done under protocol 01-M-0254.

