#### 7.2 PARTICIPANT DISCONTINUATION/WITHDRAWAL FROM THE STUDY

Prior to removal from study, effort must be made to have all subjects complete all end of study procedures listed on the Schedule of Events.

Participants are free to withdraw from participation in the study at any time upon request.

An investigator may discontinue or withdraw a participant from the study for the following reasons:

- Significant study intervention non-compliance
- If the participant meets an exclusion criterion (either newly developed or not previously recognized) that precludes further study participation
- Subject has completed the study follow-up period
- Death
- Screen Failure

The reason for participant discontinuation or withdrawal from the study will be recorded on the Enrollment log. Subjects who sign the informed consent form and are randomized but do not receive the study intervention may be replaced. Subjects who sign the informed consent form, and are randomized and receive the study intervention, and subsequently withdraw, or are withdrawn or discontinued from the study, will not be replaced.

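### Sections 6.1.2 and 8.3 remove patients who cannot tolerate 50 mg/day from the study, while 7.1 keeps them in; the mandated exit avoidably loses their week-3 MADRS

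*Combined protocol and SAP*

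**What the plan says.** Section 6.1.2 gives the rule for intolerance at the lower dose: "Subjects who are unable to tolerate the lowest allowable dose of study medication (50 mg/day) will be discontinued from the study". Section 8.3 repeats it word for word. Section 8.3 also sends everyone who discontinues the study to short-term standard treatment or another research protocol, and no further study ratings are scheduled for them.

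Section 7.1 opens with the opposite default: "Discontinuation from TS-161 does not mean discontinuation from the study, and remaining study procedures should be completed as indicated by the study protocol". It makes no exception for intolerance at 50 mg/day. Its list of reasons for which an investigator may, but need not, withdraw a patient includes adverse events and "Participant unable to receive TS-161 for 3 weeks". It also asks, as far as possible, that "data to be collected at the time of study intervention discontinuation are those intended for the final day of the study". Section 7.2 adds that before removal "effort must be made to have all subjects complete all end of study procedures listed on the Schedule of Events". Dosed patients who leave, in its words "and subsequently withdraw, or are withdrawn or discontinued from the study, will not be replaced".

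Section 9.4.2 makes the drug effect at 3 weeks the primary contrast. It comes from a mixed model with time as a factor, fitted by likelihood without imputation. Section 9.3 says analyses follow the intent-to-treat principle. Section 1.4 puts the end-of-study MADRS in the Day 56 row, which is also week 3 of Condition 2. The only timing tolerance is in the footnotes to 1.3: "Allow up to 3 days on procedures scheduled on different days to accommodate changes to the schedule".

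**The concern.** Two investigators could treat the same patient differently and each cite the protocol. One would end participation under 6.1.2; the other would keep rating under 7.1. The 7.1 wording also names TS-161, although under the blind nobody on the unit knows whether the capsule being stopped is TS-161 or placebo.

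What is at stake is the week-3 score. Under mandated exit it is not taken, and the reason is plausibly related to treatment: section 2.2.10.5 reports that nausea, vomiting, dizziness, headache and abnormal dreams rose with dose in Phase 1. Likelihood estimation copes with missing scores under assumptions about why they are missing. It does not recover a rating that could have been taken. A rating taken off drug can be set aside later in an on-drug analysis; a rating never taken cannot be supplied.

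A smaller matter is that the MADRS sought at exit has no assigned analysis visit.

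**Working it through.** **1. The instructions side by side, for a patient who fails 50 mg/day**
- 6.1.2 and 8.3: leaving the study is mandatory.
- 7.1: stay and complete the remaining procedures; withdrawal is at the investigator's discretion.
- Neither refers to the other.

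**2. The plan's own sample size (9.2), to see whether power is the issue**
- Inputs: d = 0.70, two-sided alpha 0.05, paired means, 20 patients for 80% power, 25 recruited, 25% attrition.
- Power = P(|T| > t(0.975, n − 1)), where T is noncentral t with n − 1 degrees of freedom and noncentrality d√n.
- n = 20: noncentrality 0.70 × √20 = 3.13, power 84.4%. n = 19: 82.3%. n = 18: 79.9%. The smallest n giving 80% is 19, so the stated 20 is reproduced to within one patient and is slightly conservative.
- Attrition: 25 × (1 − 0.25) = 18.75 pairs, or roughly 80% to 82% power. Section 9.2 counts dropouts during the double-blind crossover in that 25%. Intolerance exits should therefore not be subtracted again from 20 unless they exceed the allowance.

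**3. Week-3 scores lost per exit**
- Exit in Condition 1: 2 lost (that condition and the one never entered). Continued rating recovers 1, or up to 2 if the patient also crosses over.
- Exit in Condition 2: 1 lost. Continued rating recovers it and completes the pair.

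**4. How far an exit rating is from week 3**
- Dosing runs Days 0 to 20, which is 21 days. Week 3 is Day 21 (Day 56 in Condition 2).
- Edge of the 3-day allowance: 21 − 3 = Day 18 and 56 − 3 = Day 53.
- An exit on Days 0 to 17, that is 18 of 21 dosing days, gives a rating more than 3 days before week 3.

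**5. Nearest-visit assignment for early ratings (scheduled Days 3, 7, 14, 21)**
- Day 17 is 3 days from Day 14 and 4 from Day 21, so it goes to Day 14. Day 18 is 4 and 3 days away, so it goes to Day 21. A nearest-visit rule and the 3-day edge therefore agree at Day 18.
- Day 4 goes to Day 3, not Day 7. Day 5 is 2 days from each and needs a tie-break, which does not touch the primary contrast.

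**6. Evidence on how often this will happen (2.2.10.5)**
- The 10-day multiple-dose part had 6 active patients per dose. Both active-arm discontinuations due to adverse events were at 150 mg, above this trial's maximum. So there were 0 of 6 at 50 mg and 0 of 6 at 100 mg, or 0 of 12, against 1 of 6 on placebo.
- None of this measures failing 50 mg after a dose reduction over three weeks.

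**The case against.** The strongest reply is that nothing truly conflicts: 6.1.2 and 8.3 are specific rules for one event, 7.1 is the general default, and its own list allows withdrawal for the same reasons. That reading is reasonable, and a reader who infers that the protocol gives no answer goes too far. But it settles the conflict in favour of exit, which is the option that leaves week 3 uncollected.

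A reader might also infer that an exit score will be analysed as week 3, because it shares a row with Day 56. The documents do not support that. The row is a collection label, it makes no sense for a Condition 1 exit, and 9.4.2 fixes the hypothesis on the value at 3 weeks and excludes imputation. What remains is only that no sentence says which visit the score belongs to.

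Third, rating patients off drug is a choice of estimand, not the correction of an error. That stands, and it is not a choice made for power. If 1 of 20 patients stops on TS-161 and then shows no effect (an assumption, with the SD unchanged), the mean difference falls to 7.5 × 0.95 = 7.125, d = 0.665 and power is 80.5%, against 82.3% with that pair dropped. The case for retention is that it fits the intent-to-treat principle in 9.3 and the default in 7.1. The sensitivity analysis serves readers who want the on-drug answer.

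Fourth, continued rating may delay treatment, a risk that 2.3.1.3 names. That also stands, and it is why the fix needs a clinical opt-out.

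**Conclusion.** The point holds as a cheap improvement. The protocol gives two instructions for patients who cannot tolerate 50 mg/day, and the mandatory one forgoes the primary-time-point rating in patients who are already inpatients. The loss is 1 or 2 week-3 scores per affected patient. How many patients that means is unknown and probably small, since Phase 1 gives no direct rate and its data at 50 to 100 mg are reassuring but thin.

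A reader might infer that the primary result is biased or the trial underpowered. Neither follows. No bias is quantified, earlier ratings still enter the mixed model, and exits within the 25% allowance leave power at about the stated 80%. That the missingness is treatment-related is a plausible inference from the Phase 1 dose trends, which include 150 mg; it has not been shown at the doses used here.

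**What to change.** - **6.1.2 and 8.3:** replace study exit with stopping study drug, and continue scheduled MADRS ratings through week 3 of that condition (Day 21 or Day 56) where clinically acceptable and until standard treatment starts.
- **7.1:** write study drug in place of TS-161.
- **Crossover:** state whether a patient who stops in Condition 1 goes on to Condition 2. Either answer is acceptable.
- **Sensitivity:** add one analysis omitting ratings taken after study drug was stopped.
- **9.4.2 (minor clarification):** assign an early-termination MADRS to the nearest scheduled visit by actual study day, keep the scheduled rating if both exist, and never assign it to week 3 if taken before Day 18 or Day 53. Name a tie-break for Day 5 and its Condition 2 counterpart, Day 40.

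The cost is amendment wording and at most 7 post-dose ratings per affected condition (230 minutes and Days 1, 2, 3, 7, 14 and 21). At about 20 minutes each (8.4.1), that is at most 7 × 20 = 140 minutes. The real downside is a possible further wait for standard treatment, at most the rest of the 3 weeks. The clinical opt-out limits that wait, so some week-3 scores may still be missing.

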#### 7.2 PARTICIPANT DISCONTINUATION/WITHDRAWAL FROM THE STUDY

Prior to removal from study, effort must be made to have all subjects complete all end of study procedures listed on the Schedule of Events.

Participants are free to withdraw from participation in the study at any time upon request.

An investigator may discontinue or withdraw a participant from the study for the following reasons:

- Significant study intervention non-compliance
- If the participant meets an exclusion criterion (either newly developed or not previously recognized) that precludes further study participation
- Subject has completed the study follow-up period
- Death
- Screen Failure

The reason for participant discontinuation or withdrawal from the study will be recorded on the Enrollment log. Subjects who sign the informed consent form and are randomized but do not receive the study intervention may be replaced. Subjects who sign the informed consent form, and are randomized and receive the study intervention, and subsequently withdraw, or are withdrawn or discontinued from the study, will not be replaced.

#### 7.3 LOST TO FOLLOW-UP

This section is not applicable as this is an inpatient protocol.

#### 8 STUDY ASSESSMENTS AND PROCEDURES

#### 8.1 SCREENING PROCEDURES

Prior to consenting to this study, subjects will have undergone screening under protocol 01-M-0254, "The Evaluation of Patients with Mood and Anxiety Disorders and Healthy Volunteers". Psychiatric history and diagnosis of MDE will be made using the SCID-P (First, Spitzer et al. 2001) as well as DSM-IV or DSM-5 diagnostic criteria. Subjects who meet DSM-IV or DSM-5 criteria for major depressive episode (without psychotic features) must have a score of ≥20 on the MADRS within one week of the start of Phase I and upon entry into Study Phase II. Subjects who previously enrolled in and completed studies at the ETPB may be enrolled in this protocol.

We will require that all subjects have physical examinations and specific laboratory tests (e.g. Acute Care Panel, CBC+Diff, Hepatic Panel, LFT, TFT, urinalysis, urine pregnancy, urine toxicology, HIV). Results of these tests will identify patients who should be excluded because of active medical problems or substance abuse that might affect clinical phenomenology or make participation in the protocol unsafe. Subjects are expected to meet all other eligibility criteria to be enrolled in the study. Protocol 01-M-0254 allows for the sharing of collected data, including history and physical exams, structural neuroimaging studies, and lab testing.

